Appendix II – Interpreting Adverse Event Causality

The following factors should be considered when deciding if there is a "reasonable possibility" that an adverse event may have been caused by the study medication.

- Time Course. Exposure to suspect study medication. Has the subject actually received the suspect study medication? Did the adverse event occur in a reasonable temporal relationship to the administration of the suspect study medication?
- Consistency with known study medication profile. Was the adverse event consistent with
 the previous knowledge of the suspect study medication (pharmacology and toxicology)
 or drugs of the same pharmacological class? OR Could the adverse event be anticipated
 from its pharmacological properties?
- Dechallenge experience. Did the adverse event resolve or improve on stopping or reducing the dose of the suspect study medication?
- No alternative cause. The adverse event cannot be reasonably explained by another etiology such as the underlying disease, other drugs, other host or environmental factors
- Rechallenge experience. Did the adverse event reoccur if the suspected study medication was reintroduced after having been stopped Laboratory tests. A specific laboratory investigation (if performed) has confirmed the relationship?

A "reasonable possibility" could be considered to exist for an adverse event where one or more of these factors exist.

In contrast, there would not be a "reasonable possibility" of causality if none of the above criteria apply or where there is evidence of exposure and a reasonable time course, but any dechallenge (if performed) is negative or ambiguous or there is another more likely cause of the adverse events.

In difficult cases, other factors could be considered such as:

- Is this a recognized feature of overdose of the study medication?
- Is there a known mechanism?

Ambiguous cases should be considered as being a "reasonable possibility" of a causal relationship unless further evidence becomes available to refute this. Causal relationship in cases where the disease under study has deteriorated due to lack of effect should be classified as no reasonable possibility.

Verona Pharma plc CONFIDENTIAL Page 67 of 67

This document describes the rules and conventions to be used in the presentation and analysis of efficacy and safety data for protocol RPL554-CO-203. It describes, in detail, the data to be summarized and analyzed, including specifics of the statistical analyses to be performed.

This statistical analysis plan is based on the final protocol version 2.0, dated 18th of April 2017.

2. Study objectives

The purpose of this study is to investigate the dose response of RPL554 in patients with Chronic Obstructive Pulmonary Disease (COPD) over 4 weeks. Clinical practice indicates that this length of time should allow for the study of the bronchodilator response (measured predominantly by peak FEV₁) and the anti-inflammatory response (measured predominantly by trough FEV₁).

2.1. Primary objective

The primary objective of this study is to investigate the placebo-corrected effect of RPL554 administered by nebulizer on change from baseline in peak FEV₁ (maximum over 3 hours following dosing) over 4 weeks when administered to patients with moderate to severe COPD.

2.2. Secondary objectives

The secondary objectives of this study are as follows:

- To investigate the placebo-corrected effect of RPL554 administered by nebulizer on change from baseline in morning trough FEV₁ over 4 weeks when administered to patients with moderate to severe COPD
- To investigate the bronchodilator placebo-corrected effect of RPL554 administered by nebulizer on AUC_{0-12 hours} FEV₁ after 4 weeks of dosing
- To investigate the single-dose bronchodilator placebo-corrected effect of RPL554 on peak and average FEV₁ at Visit 2 (first dose)
- To investigate the bronchodilator placebo-corrected effect of RPL554 on peak and average FEV₁ over 3 hours at Visits 3 to- 6 (Weeks 1 to 4)
- To investigate the placebo-corrected effects of RPL554 on COPD symptoms, as measured by daily diary (E-RS from the Exacerbations of Chronic Pulmonary Disease Tool Patient-Reported Outcomes [EXACT-PRO+], Transition Dyspnea Index [TDI], St George's Respiratory Questionnaire – COPD specific [SGRQ-C], Medical Research Council [MRC] scale, and patient global assessment of change (PGAC)
- To investigate the safety of RPL554 when administered for 4 weeks in patients with COPD, as measured by adverse events, electrocardiograms (ECGs), Holter monitoring and vital signs
- To compare the amount of rescue albuterol/salbutamol use required

2.3. Exploratory Objectives

Additional, exploratory objectives of this study are as follows:

- To compare peak and AUC_{0-12 hour} FEV₁ at the final study visit (visit 6) to baseline (Day 1)
- To correlate trough pharmacokinetics with pharmacodynamics effects

3. Study design

This is a phase IIb, randomized, double-blind, placebo-controlled, parallel group study designed to evaluate the efficacy and safety of nebulized RPL554 in patients with moderate to severe COPD over 4 weeks.

3.1. General Description

A total of approximately 400 patients between the ages of 40 and 75 years, inclusive, with a clinical diagnosis of COPD, as defined by the American Thoracic Society (ATS)/European Respiratory Society (ERS) guidelines and symptoms compatible with COPD for at least 1 year prior to screening will be enrolled.

Patients will be seen at approximately 50 sites throughout the European Union. The study comprises six visits: screening (visit 1), randomization (visit 2), and weekly visits for 4 weeks (visit 3 to visit 6, Week 1 to Week 4). Patients will be screened for eligibility (visit 1), including a reversibility test with albuterol/salbutamol between 7 and 14 days before the first dose of study medication.

3.2. Treatments

3.2.1. Treatments Administered

Patients will be randomized to either RPL554 or placebo. Those assigned to RPL554 will receive one of four active strengths, as described in the table below:

Table 1: RPL554 Doses

Substance	Dose Level (mg)	Concentration (mg/mL)
RPL554	0.75	0.3
RPL554	1.5	0.6
RPL554	3.0	1.2
RPL554	6.0	2.4
Placebo	N/A	N/A
N/A = Not Applicable		

All study medications will be administered twice daily, using a standard jet nebulizer.

3.2.2. Method of Assigning Patients to Treatment Groups

At the screening visit, the investigator will assign a unique patient number to each enrolled patient. This patient number is made up of three digits unique to each study site and 3 digits for each consecutively enrolled patient at the trial site, provided an informed consent form is signed by the patient. This number should be entered into the electronic data capture (EDC) system and maintained throughout the study. Once the patient meets inclusion and exclusion criteria, the study site will request the study medication assignment using the Interactive Response System (IXRS).

3.2.3. Blinding

This is a randomized, double-blind, placebo-controlled study. Placebo will be similar to

RPL554, except for the omission of the active ingredient. Because a visually matching placebo could not be developed, the dosing cup on each nebulizer administered at the study center will be obscured with opaque tape to visually blind the study medication.

3.3. Determination of Sample Size

The standard deviation for peak FEV1 is estimated to be 250 mL. With a 2-sided test at a 5% significance level and 80 evaluable patients per group, there will be an 80% power to detect a true difference of 111 mL between any two treatments. This detectable limit has been considered sufficient to conclusively identify a minimal effective dose of RPL554. Thus 80 patients per group will be randomized for a total of 400 patients.

3.4. Changes in the Conduct of the Study or Planned Analyses

- The method for analysis the primary efficacy endpoint has been changed from LOCF ANCOVA to mixed model for repeated measures (MMRM). The change was led by the superiority of MMRM with respect to LOCF in avoiding some type of bias as suggested by Siddiqui et al. (Siddiqui O, 2009)
- Introduction of Per Protocol analysis set. This is an analysis set of interest for a phase II study.

3.5. Analysis Sets

All randomized analysis Set: includes all randomized patients

Safety Analysis Set: includes all patients who receive at least one dose of investigational product during the study. It is a subset of all randomized analysis set.

Full Analysis Set: includes all randomized patients, who receive at least one dose of investigational product during the study and with at least one post/treatment efficacy data assessment among spirometry EXACT-PRO questionnaire, SGRQ, TDI PGAC and MRC. It is a subset of the safety analysis set.

Per-Protocol Analysis Set: includes all patients who do not have pre-specified major protocol deviations which can affect the efficacy outcome or the treatment of the subject (see section 3.6). It is a subset of the safety analysis set.

Use of the analysis set

	All-Randomized set	Full Analysis Set	Safety Analysis Set	Per-Protocol Analysis Set
Disposition of patients	X			
Protocol deviations	X			
Demographic and other baseline characteristics	X			
Medical history	X			
Prior and concomitant medication			X	
Treatment compliance and extent of exposure			X	

Efficacy: Primary endpoint		X		X
Efficacy: Secondary endpoints		X		X
Efficacy: Exploratory endpoints		X		X
Safety			X	
Pharmacokinetic			X	

The number and percentage of patients within each of these analysis sets will be presented by treatment group and overall.

3.6. Major Protocol Deviations

Major protocol deviations will be defined in a separate document that will be finalized before database lock.

Patients with major protocol deviations will be identified by a clinical review of the data prior to database lock to the extent possible in light of restrictions due to blinding of study personnel to treatment assignments.

A summary of major protocol deviations will be presented by treatment group for all randomized patients.

3.7. General Methodology

Summary statistics will be presented to give descriptions of patients and an overview of efficacy and safety results. All analysis tables will include summaries for all five treatment groups: RPL554 0.75 mg BID, RPL554 1.5 mg BID, RPL554 3.0 mg BID, RPL554 6.0 mg BID, Placebo BID. Categorical parameters will be summarized with number of observations and percentage of patients in each category. Continuous parameters will be summarized using number of observations, mean, standard deviation (SD), median, minimum and maximum.

Unless specified otherwise, all statistical tests will be two-sided. All p-values will be rounded to three decimal places; p-values less than 0.001 will be presented as '<0.001' and greater than 0.999 will be presented as '>0.999' in all tables.

All available data from all patients will be listed.

3.7.1. Baseline

Unless otherwise specified, baseline is defined as the last non-missing measurement taken prior to study medication start date (including unscheduled assessments). In the case where the last non-missing measurement and the study medication start date coincide (and time is either not collected or missing), that measurement will be considered pre-baseline, but Adverse Events (AEs) and medications commencing on the reference start date will be considered post-baseline.

3.7.2. End of Study

This will be visit 6.

3.7.3. Visit Windows

No visit windows will be applied in this study and the scheduled assessments will be reported and analyzed as per CRF collection.

3.7.4. Duration

For the purposes of calculating durations expressed in months, a month will be considered as one-twelfth of a year, or $365.25 / 12 = 30.4375$ days.

As for duration in days, the calculation will go as follows:

- (stop date – start date) + 1 if start date is same as first dose date or later;
- (stop date – start date) if start date is before first dose date.

3.7.5. Treatment period

Treatment period is defined as the time elapsed between the first and last dose intake date plus 1 day. Assessments will be included in the safety and efficacy analysis if performed during the treatment period.

3.8. Handling of Dropouts or Missing Data

3.8.1. Missing data in efficacy analysis

MMRM model will be used as a strategy to deal with missing data.

Last observation carried forward approach (LOCF) will be used a sensitivity analysis of the primary endpoint only.

No other imputation will be applied.

3.8.2. Missing data in safety analysis

Any missing safety parameter will be considered missing for purposes of any summary statistics and analysis.

3.8.3. Partial Date Imputation

Dates are essential for the classification of AEs as treatment-emergent and medications as having been taken prior to the start of study medication and/or concomitantly with study medication.

3.8.4. Partial Dates for AEs

Adverse event start date (references to month are the month of the AE start date):

1. If only month and year are known and study medication started during that month then set start date equal to study medication start date.
2. If month and year are known and study medication started prior to or after that month then set start date equal to 1st day of month.
3. If only year is known, and it is the same as study medication start year, assume it is the study medication start date/year. If it is different from study medication start year, assume it is the first day of the year.
4. If full start date (i.e. day, month, and year are missing) is unknown impute start date as the study medication start date. If imputed start date is greater than stop date, it will be imputed as stop date.

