7.6.2 Recording and Assessing Adverse Events

All adverse events, whether reported spontaneously by the patient, in response to open questioning on treatment days or observed by the Investigator or his/her staff, will be recorded from informed consent until the Telephone Follow-up (2 weeks after Visit 6b).

The start and stop time will be recorded and adverse events will be assessed by the Investigator for the following:

7.6.2.1 *Severity*

Mild: Resolved without treatment

Moderate: Resolved or was tolerated with specific treatment without affecting

study activities

Severe: Did not resolve or was not tolerated with treatment

7.6.2.2 *Chronicity*

Single occasion: Single event with limited duration

Intermittent: Several episodes of an event, each of limited duration Persistent:

Event which remained indefinitely

Verona Pharma plc CONFIDENTIAL Page 49 of 67

7.6.2.3 *Causality*

The Investigator will assess causal relationship between the study medication and each adverse event, and answer "yes" or "no" to the question, "Do you consider that there is a reasonable possibility that the event may have been caused by the study medication?"

For SAEs, causal relationship will also be assessed for study procedures, additional study medication, and other medication. Note that for SAEs that could be associated with any study procedure, the causal relationship is implied as "yes".

A guide to the interpretation of the causality question is found in Appendix II.

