6.1. Adverse Events

Treatment Emergent Adverse Events (TEAEs) are defined as all AEs which start after the first dose of study medication, or start prior to first dose of study medication and worsen, based on the investigator assessment of severity, on or after first dose of study medication.

Adverse events with completely missing onset dates will also be considered as treatment emergent. If any AE records contain only partial dates, these will be handled by imputation, as described in Section 3.8.4.

Table summaries will be produced summarizing AEs in the following ways:

- TEAEs
- TEAEs classified by maximum severity
- TEAEs classified with relationship to study medication
- TEAEs leading to study discontinuation
- Serious TEAEs
- Serious TEAEs classified by maximum severity
- Serious TEAEs classified with relationship to study medication
- Serious TEAEs leading to study discontinuation
- TEAEs with outcome death

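### SAP 6.1 counts every adverse event with no onset date as treatment-emergent, even one known to have stopped before the first dose

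*SAP*

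**What the plan says.** Protocol 7.6.2 has adverse events collected with start and stop times, and says they "will be recorded from informed consent until the Telephone Follow-up". Events that begin and end before the first dose will therefore be in the database.

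SAP 3.8.4 gives four numbered rules for incomplete onset dates. Three can place the onset on the first-dose date:

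- Item 1 (month and year known): "If only month and year are known and study medication started during that month then set start date equal to study medication start date".
- Item 3 (year only): "If only year is known, and it is the same as study medication start year, assume it is the study medication start date/year".
- Item 4 (nothing known): an onset that "is unknown impute start date as the study medication start date". Item 4 then closes with "If imputed start date is greater than stop date, it will be imputed as stop date".

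That closing sentence is the only stop-date check for adverse events. The section has no rule for a partial stop date.

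SAP 6.1 sets treatment-emergent status. TEAEs are "defined as all AEs which start after the first dose of study medication", or events that began earlier and worsened on or after that dose. It adds: "Adverse events with completely missing onset dates will also be considered as treatment emergent". For the rest: "If any AE records contain only partial dates, these will be handled by imputation, as described in Section 3.8.4". SAP 3.7.1 treats an adverse event that begins on the reference start date as post-baseline.

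**The concern.** Placing an uncertain onset on treatment is a sensible cautious default. The reason for it goes once the stop date is known to precede the first dose, because such an event cannot have emerged on treatment, nor can it have worsened on treatment. The closing sentence of item 4 shows that the SAP means to use the stop date. But 6.1 decides the status of an event with no onset date without looking at the stop date, so the check in item 4 alters a date in the dataset and nothing in the tables.

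The accuracy of the safety tables is at stake: all nine adverse-event summaries listed in SAP 6.1 are restricted to TEAEs. There is also an internal mismatch. SAP 3.8.3 presents dates as the basis for classifying events as treatment-emergent, yet here the imputed date and the classification disagree.

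**Working it through.** The plan has no figure to reproduce on this point. The check applies the rules to a test record and then asks how far items 1 and 3 could reach.

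**Step 1. Test record.** The event stopped on 12 September 2017 and the first dose was on 20 September 2017, so the event ended 8 days before exposure. The onset is recorded at three levels of completeness. The closing sentence of item 4 is read in two ways: narrow (item 4 only, where it is printed) and wide (all items).

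| Onset recorded as | Rule | Narrow: imputed onset | Narrow: status | Wide: imputed onset | Wide: status |
|---|---|---|---|---|---|
| September 2017 | item 1 | 20 Sep | TEAE | 12 Sep | not TEAE |
| 2017 | item 3 | 20 Sep | TEAE | 12 Sep | not TEAE |
| nothing | item 4, then 6.1 | 12 Sep | TEAE by 6.1 | 12 Sep | TEAE by 6.1 |

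The event is wrongly counted in 3 of 3 cases on the narrow reading and in 1 of 3 on the wide reading.

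**Step 2. The bottom row.** Item 4 first gives 20 September and its closing sentence then moves this to 12 September. By date alone the event is pre-treatment. SAP 6.1 nevertheless classes it as treatment-emergent because the onset was wholly missing, and sends only partial dates to 3.8.4. The result does not depend on how the closing sentence is read.

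**Step 3. The top two rows.** On the narrow reading the imputed onset is 8 days after the event's own stop date. The TEAE definition asks for a start after the first dose, whereas the imputed onset equals the first-dose date. SAP 3.7.1 closes that gap by making an event that starts on that date post-baseline.

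**Step 4. Reach of items 1 and 3, if the date is partial.** Assumptions: first doses spread evenly over the planned study period, June 2017 to January 2018 (245 days, 8 months); onsets spread evenly over the L days before the first dose; L = 7 or 14, the screening limits in Protocol 6.2. Each month boundary puts L(L+1)/2 of the dose-day and onset-day pairs into the previous month.

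- Same month, L = 7: 1 − (8 × 28)/(245 × 7) = 1 − 224/1715 = 87%.
- Same month, L = 14: 1 − (8 × 105)/(245 × 14) = 1 − 840/3430 = 76%.
- Same year (one year boundary), L = 7: 1 − 28/1715 = 98%.
- Same year, L = 14: 1 − 105/3430 = 97%.

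So if a pre-dose event has a partial onset, items 1 and 3 will usually apply to it. These shares say nothing about how often onsets are partial, and the documents give no such rate.

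**Step 5. After the fix.** If the stop-date check covers every imputed onset and 6.1 has the exception, the test event is treatment-emergent in 0 of 3 cases.

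**The case against.** **The stop-date sentence may be meant for all items.** Its wording is general, it closes the section, and it does not mention wholly missing dates. In text read from a PDF, its position inside item 4 is weak evidence. This objection stands: a reader might infer that items 1 and 3 certainly misplace events, but the documents support that only on the narrow reading. The wide reading leaves the 6.1 problem untouched.

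**SAP 6.1 is an express instruction.** A reader might infer that 3.8.4 and 6.1 leave the programmer free to count the event or not. They do not: 3.8.4 assigns a date and 6.1 assigns the status. The fault is that the instruction lacks an exception, not that it leaves a choice.

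**Affected records will be rare.** A record needs a known pre-dose stop date together with an incomplete onset. Start and stop times are recorded, patients are asked about adverse events before dosing at Visit 2 (Protocol 6.3.1), and data are validated and queried (Protocol 8.3). This stands.

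**Serious and related events are unlikely routes.** Serious events are reported within 24 hours of awareness (Protocol 7.6.3) and listed by patient (SAP 6.1.1), so a wholly unknown onset with a known pre-dose stop is remote. The causality guide in Protocol Appendix II first asks whether the patient had received the drug, so an event that ended before dosing should not be judged related. One misplaced event would add 1/80 = 1.25 percentage points to an arm of 80, but the documents give no reason to expect one among serious or related events.

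**Conclusion.** The point holds as a minor flaw in the safety rules. For a wholly missing onset, SAP 6.1 gives the wrong status to any event known to have stopped before the first dose, on either reading of 3.8.4. For a partial onset in the dosing month or year, the same error occurs only if the stop-date sentence is confined to item 4.

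For an affected record the misclassification is complete. The number of affected records cannot be derived from the documents and is probably small.

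A reader might infer a distorted comparison between doses and placebo. The documents do not support that. The events in question begin and end before the first dose, the date rules are the same in every arm, and allocation is equal and random, so the extra events should fall about evenly. The effect is a slight inflation of TEAE counts, with some noise. Efficacy analyses are not affected.

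**What to change.** 1. **SAP 3.8.4:** take the stop-date sentence out of item 4 and make it a separate rule that applies to every imputed onset under items 1 to 4.
2. **SAP 6.1:** amend the sentence on missing onsets to read: *AEs with completely missing onset dates are treatment-emergent unless the stop date is known to be before the first dose.*
3. **Partial stop dates:** state that an event is pre-treatment only if its latest possible stop date is before the first dose. Otherwise the cautious default stays.

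SAP 3.8.5 applies the 3.8.4 pattern to medication start dates, so its wording should be checked in the same edit.

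The cost is a few sentences and a small programming change. No new data are needed, and the default for events of truly uncertain timing is kept.
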